4.4. Randomization

Randomization will be performed for participants in Part J. For Part J, participants will be randomized in a 1:1 ratio to receive one of 2 treatments. Randomization will not be blinded.

4.5. Blinding and Unblinding

Not applicable.

4.6. External Comparator for Part F Cohort 1 - Study mRNA-1273-P201 Part B Subjects

Study mRNA-1273-P201 (P201) Part B, is the Open-Label Interventional Phase of the study, and was prompted by the authorization of a COVID-19 vaccine under an EUA. In Part B, all participants who previously received 1 or 2 injections of mRNA-1273 (50 µg or 100 µg) vaccine were able to receive a single booster dose of mRNA-1273 (50 µg). A total of approximately 150 participants in the P201 50 µg mRNA-1273 booster arm who were primed with 2 doses of 100 µg mRNA-1273 will serve as an external comparator for the P205 Part F 50 µg mRNA-1273.529 arm (Cohort 1).

5. Analysis Sets

The following analysis sets are defined: All Enrolled Set, Full Analysis Set, Per-Protocol Immunogenicity Set, Per-Protocol Immunogenicity Sensitivity Set, Per-Protocol Immunogenicity SARS-CoV-2 Negative Set, Solicited Safety Set, Safety Set, and Per-Protocol Efficacy Set. Definitions are the same across study Parts A (1, 2), B, C, D, E, F, G, H and J when applicable.

5.1. All Enrolled Set

The All Enrolled Set consists of all participants who enrolled in the study for Parts A.1, A.2, B, C, D, E, F, G, H, or were randomized for Part J.

5.2. Full Analysis Set (FAS)

The Full Analysis Set (FAS) consists of all participants who receive IP.

5.3. Per-Protocol Immunogenicity Set (PPIS)

The Per-Protocol Immunogenicity Set (PPIS) for immunogenicity consists of all P205 participants in the FAS who meet all the criteria listed below, and who were in P201 external comparator who were in the Per-Protocol Set for Part B.

mRNA-1273-P205 participants

- a) Received the planned dose of study vaccination per schedule
- b) For Parts A.1, A.2, B, C, D, F, G, H: had pre-booster and Day 29 (occurring between 21 and 42 days after vaccination) neutralizing antibody data; for Part J: had pre-booster and Day 15 neutralizing antibody data
 - Part A.1: against B.1.351 variant
 - Part A.2: against B.1.1.529 variant
 - Part B: against ancestral SARS-CoV-2
 - Part C: against B.1.617.2 variant
 - Part D: against B.1.351 variant and B.1.617.2 variant
 - Part F (Cohort 1 and Cohort 2): against B.1.1.529 variant
 - Part G: against B.1.1.529 variant
 - Part H: against BA.4/5 variant
 - Part J: against XBB.1.5 variant
- c) Had no major protocol deviations that impact key or critical data
- d) Had no previous HIV infection

mRNA-1273-P201 external comparator

Consists of P201B participants after 100 µg primary series who were in Per-Protocol Set for Part B (please refer to P201 SAP version 5.0 Section 5.6 for details).

The PPIS will be used as the primary analysis set for analyses of immunogenicity for Parts A.1, B, C, D, and J, Full Analysis Set will be used for Part E binding antibody descriptive summary.

5.4. Per-Protocol (PP) Immunogenicity Sensitivity Set

For Parts A.1, A.2, B, C, D, F, G, H, the PP Immunogenicity Sensitivity Set for immunogenicity may be used for sensitivity analysis and will consist of participants who meet all requirements for the PPIS with the exception of the time window for Day 29 neutralizing antibody data.

mRNA-1273-P205 participants

- a) Received the planned dose of study vaccination per schedule
- b) Had pre-booster and Day 29
 - Part A.1: against B.1.351 variant
 - Part A.2: against B.1.1.529 variant
 - Part B: against ancestral SARS-CoV-2
 - Part C: against B.1.617.2 variant
 - Part D: against B.1.351 variant and B.1.617.2 variant
 - Part F (Cohort 1 and Cohort 2): against B.1.1.529 variant
 - Part G: against B.1.1.529 variant
 - Part H: against BA.4/5 variant
- c) Had no major protocol deviations that impact key or critical data
- d) Had no previous HIV infection

5.5. Per-Protocol Immunogenicity SARS-CoV-2 Negative Set (PPIS-Neg)

The PPIS-Neg Set consists of P205 participants who meet all requirements for the PPIS and have no serologic or virologic evidence of SARS-CoV-2 infection at baseline and P201B participants who were in the Per-Protocol Set for Part B.

mRNA-1273-P205 participants

- a) Received the planned dose of study vaccination per schedule
- b) For Parts A.1, A.2, B, C, D, F, G, H: had pre-booster and Day 29 (occurring between 21 and 42 days after vaccination) neutralizing antibody data; for Part J: had pre-booster and Day 15 neutralizing antibody data
 - Part A.1: against B.1.351 variant
 - Part A.2: against B.1.1.529 variant
 - Part B: against ancestral SARS-CoV-2
 - Part C: against B.1.617.2 variant
 - Part D: against B.1.351 variant and B.1.617.2 variant
 - Part F (Cohort 1 and Cohort 2): against B.1.1.529 variant
 - Part G: against B.1.1.529 variant
 - Part H: against BA.4/5 variant
 - Part J: against XBB.1.5 variant

- c) Had no major protocol deviations that impact key or critical data
- d) Had no previous HIV infection
- e) Have no serologic or virologic evidence of SARS-CoV-2 infection at baseline (ie, who are SARS-CoV-2 negative, defined by both negative RT-PCR test for SARS-CoV-2 and negative serology test based on bAb specific to SARS-CoV-2 nucleocapsid)

mRNA-1273-P201B external comparator

Consists of P201B participants after 100 µg primary series who were in Per-Protocol Set for Part B (please refer to P201 SAP version 5.0 Section 5.6 for details).

The PPIS-Neg Set will be used as the primary analysis set for analyses of immunogenicity for Parts A.2, F (Cohort 1), F (Cohort 2), G, and H.

5.6. Solicited Safety Set

The Solicited Safety Set consists of all participants who receive IP and contribute any solicited AR data.

The Solicited Safety Set will be used for the analyses of solicited ARs. Participants will be included in the study arm corresponding to the dose of IP that they actually received.

5.7. Safety Set

The Safety Set consists of all participants who receive IP.

The Safety Set will be used for all analyses of safety except for the solicited ARs. Participants will be included in the study arm corresponding to the dose of IP that they actually received.

5.8. Per-Protocol (PP) Efficacy Set

The PP Efficacy Set consists of all participants in the FAS who received the planned dose of study vaccination, who are SARS-CoV-2 negative pre-booster (ie, have a negative RT-PCR test for SARS-CoV-2 and a negative serology test based on bAb specific to SARS-CoV-2 nucleocapsid pre-booster), and have no major protocol deviations that impact key or critical data.

The PP Efficacy Set will be used as the primary analysis set for analyses of efficacy unless otherwise specified.

6. Statistical Analysis

6.1. General Considerations

Please refer to the protocol for Schedule of Events (SoE).

Continuous variables will be summarized using the following descriptive summary statistics: the number of subjects (n), mean, standard deviation (SD), median, minimum (min), and maximum (max).

Categorical variables will be summarized using counts and percentages.

Baseline value, unless specified otherwise, is defined as the most recent non-missing measurement (scheduled or unscheduled) collected before the dose of IP in this study. Pre-booster and baseline are used interchangeably for the study arms in P205. For immunogenicity tests, the baseline is defined as the most recent non-missing measurement (scheduled or unscheduled) collected before the dose of IP.

For the summary statistics of all numerical variables, unless otherwise specified, the display precision will follow programming standards. Refer to [Appendix A](#) for variable display standards.

When count data are presented, the percentage will be suppressed when the count is zero in order to draw attention to the non-zero counts. “Missing” will be included in count tabulations where specified on the shells to account for dropouts and missing values. The denominator for all percentages will be the number of subjects in the corresponding group, unless otherwise specified.

Pre-booster SARS-CoV-2 status is determined by using virologic and serologic evidence of SARS-CoV-2 infection on or before Day 1 (pre-booster).

Positive SARS-CoV-2 status at pre-booster is defined as a positive RT-PCR test for SARS-CoV-2, and/or a positive serology test based on bAb specific to SARS-CoV-2 nucleocapsid (as measured by Roche Elecsys Anti- SARS-C oV-2 assay) on or before Day 1.

Negative status at pre-booster is defined as a negative RT-PCR test for SARS-CoV-2 and a negative serology test based on bAb specific to SARS-CoV-2 nucleocapsid (as measured by Roche Elecsys Anti- SARS-CoV-2 assay) on or before Day 1.

Study day relative to the injection will be calculated as follows:

- a) study day prior to the injection will be calculated as: date of assessment/event – date of the injection;
- b) study day on or after the date of the injection will be calculated as: date of assessment/event – date of the injection + 1;

For calculation of antibody levels/titers, antibody values reported as below LLOQ will be replaced by $0.5 \times \text{LLOQ}$. Values that are greater than the upper limit of quantification (ULOQ) will be converted to the ULOQ if actual values are not available. Missing results will not be imputed unless specified otherwise.

The following **analysis periods for safety analyses** will be used:

- Up to 28 days after vaccination: from the day of vaccination (Day 1) and continues through the earliest date of (the day of vaccination and 27 subsequent days, the day of study discontinuation). This analysis period will be used as the primary analysis period for safety analyses including unsolicited AEs, except for solicited ARs, unless specified otherwise.
- Throughout the study: from the day of vaccination (Day 1) and continues through the earliest date of (study completion, discontinuation from the study, or death).

Unscheduled visits: Unscheduled visit measurements will be included in the analysis as follows:

- In scheduled visit windows per specified visit windowing rules.
- In the derivation of baseline/last on-treatment measurements.
- In the derivation of maximum/minimum on-treatment values and maximum/minimum change from baseline values for safety analyses.
- In individual subject data listings as appropriate.

Visit windowing rules: The analysis visit windows for protocol-defined visits are provided in [Appendix B](#).

Incomplete/missing data:

- Imputation rules for missing or incomplete days of medications, non-study vaccinations and procedures are provided in [Appendix C](#).
- Imputation rules for missing or incomplete AE dates are provided in [Appendix D](#).
- If the laboratory results are reported as below the LLOQ (e.g., <0.1), the numeric values will be imputed by $0.5 \times \text{LLOQ}$ for the calculation of summary values. If the laboratory results are reported as greater than the ULOQ (e.g., >3000), the numeric values will be imputed by ULOQ in the summary if actual values are not available.
- Other incomplete/missing data will not be imputed, unless specified otherwise.

Treatment groups

- Part A.1: 50 µg of mRNA-1273.211 and 100 µg of mRNA-1273.211
- Part A.2: 50 µg of mRNA-1273.214
- Part B: 100 µg of mRNA-1273
- Part C: 50 µg of mRNA-1273.617.2 and 100 µg of mRNA-1273.617.2
- Part D: 50 µg of mRNA-1273.213 and 100 µg of mRNA-1273.213
- Part E: 100 µg of mRNA-1273.213
- Part F Cohort 1: 50 µg of mRNA-1273.529
- Part F Cohort 2: 50 µg of mRNA-1273.529 and 50 µg of mRNA-1273
- Part G: 50 µg of mRNA-1273.214
- Part H: 50 µg of mRNA-1273.222
- Part J: 50 µg of mRNA-1273.815 and 50 µg of mRNA-1273.231

External comparator

- 50 µg of mRNA-1273 (booster arm primed with 2 doses of 100 µg mRNA-1273 from Study mRNA-1273-P201 used as an external comparator for P205 Part F Cohort 1).

Subgroup Analysis

Immunogenicity will be assessed in the following subgroups:

- Age (18 to <65, and ≥ 65 years)

- Sex (female, male)
- Pre-booster SARS-CoV-2 status (negative, positive) if there is enough of pre-booster positives
- Race (White, Black or African American, Other)
- Ethnicity (Hispanic or Latino, Not Hispanic or Latino)

Safety may be assessed for the same subgroups.

Subgroup analyses may not be performed for Part J due to small sample size.

Analyses Approach

There are multiple parts in P205, all analyses and data summaries/displays will be provided by study arm for each study part using appropriate analysis population.

Subjects Received Off-study COVID-19 Vaccine

If a participant received off-study COVID-19 vaccine, the participant's immune response and effectiveness data will be censored at the earlier date of date of off-study COVID-19 vaccine, or date of last observed in study.

All analyses will be conducted using SAS Version 9.4 or higher.

6.2. Background Characteristics

6.2.1. Subject Disposition

The number and percentage of subjects in the following categories will be summarized as defined in [Section 6.1](#) based on:

- Full Analysis Set
- Per-Protocol Immunogenicity Set
- Per-Protocol Immunogenicity Sensitivity Set
- Per Protocol Immunogenicity SARS-CoV-2 Negative Set
- Solicited Safety Set
- Safety Set
- Per-Protocol Efficacy Set

The percentage will be based on the number of subjects in the All Enrolled Set.

The number and percentage of subjects in each of the following disposition categories will be summarized based on the Full Analysis Set:

- Received the dose of IP
- Completed study
- Prematurely discontinued the study and the reason for discontinuation

This study treatment only consists of a 1-dose booster, thus discontinuation from study treatment is not applicable to this study. A subject who completed 12 months of follow up after the injection is considered to have completed the study for study parts A.1, B, C, D, E, F, and G. A subject who completed 6 months of follow up after the injection is considered to have completed the study for study parts A.2, H and J.

A subject disposition listing for participants who discontinued the study early will be provided, including informed consent, subjects who were vaccinated, subjects who completed the study, subjects discontinued from the study, with reasons for discontinuation.

6.2.2. Demographics

Descriptive statistics will be calculated for the following continuous demographic and baseline characteristics: age (years), weight (kg), height (cm), and body mass index (BMI) (kg/m^2). Number and percentage of subjects will be provided for categorical variables such as age group (18 to <65 , and ≥ 65 years), gender, race, ethnicity, pre-booster SARS-CoV-2 status, time duration from completion of primary series to booster dose, time duration from first to second booster dose (if applicable), and time duration from second to third booster dose (if applicable). The summaries will be provided based on the Safety Set and Per-Protocol Immunogenicity Set. If the subjects in two or more analysis sets are identical, only one table will be provided for such analysis sets.

6.2.3. Medical History

Medical history data will be coded by system organ class (SOC) and preferred term (PT) using the Medical Dictionary for Regulatory Activities (MedDRA).

The number and percentage of participants with any medical history will be summarized by SOC and PT based on the Safety Set. A participant will be counted only once for multiple events within each SOC and PT. SOCs will be displayed in internationally agreed

order and, within each SOC, PTs will be displayed in alphabetical order for first booster, in descending order of frequency based on the mRNA-1273 50 µg group then alphabetically for second booster, and in descending order of frequency based on the mRNA-1273.231 50 µg group then alphabetically for third booster.

6.2.4. Prior and Concomitant Medications

Prior and concomitant medications and non-study vaccination will be coded using the World Health Organization (WHO) drug dictionary (WHODD). The summary of concomitant medications will be based on the Safety Set.

A summary table of concomitant medications and non-study vaccination that continued or newly received at or after the injection through 28 days will be provided by PT in alphabetical order for first booster, in descending order of frequency based on the mRNA-1273 50 µg group then alphabetically for second booster, and in descending order of frequency based on the mRNA-1273.231 50 µg group then alphabetically for third booster.

Medications taken to prevent pain or fever will be collected on eDiary and summaries will be provided based on the Solicited Safety Set as defined in [Section 6.1](#), including within 7 days after injection, beyond 7 days after injection and after injection.

6.2.5. Study Exposure

Summary of study exposure will be summarized.

Study duration, defined as time on study from the injection/booster to study discontinuation, study completion, or last contact date, whichever occurs earlier, will be summarized.

6.2.6. Major Protocol Deviations

Major protocol deviations are a subset of protocol deviations that may significantly impact the completeness, accuracy, or reliability of the study data or that may significantly affect a subject's rights, safety, or well-being. Major protocol deviations rules will be developed and finalized before database lock.

The number and percentage of the subjects with each major protocol deviation type will be provided as defined in [Section 6.1](#) based on the FAS.

Major protocol deviations will be presented in a listing.

Select major protocol deviations are deemed to impact critical data and lead to exclusion from the Per-Protocol Immunogenicity Set or Per-Protocol Efficacy Set. Number of subjects with such major protocol deviations leading to exclusion from the PP Sets will be summarized.

6.3. Safety Analysis

Safety and reactogenicity will be assessed by clinical review of all relevant parameters including solicited ARs (local and systemic), unsolicited treatment-emergent AEs, treatment-related AEs, severe AEs, SAEs, MAAEs, AESIs, AEs leading to withdrawal from study participation, vital signs, and physical examinations-findings. Unsolicited treatment-emergent AEs will be coded by SOC and PT according to the MedDRA. The Toxicity Grading Scale for Healthy Adult and Adolescent Volunteers Enrolled in Preventative Vaccine Clinical Trials ([DHHS 2007](#)) is used in this study for solicited ARs.

Safety analyses will be based on the Safety Set, except that the Solicited Safety Set will be used for analyses of solicited AR.

6.3.1. Adverse Events

A treatment-emergent AE (TEAE) is defined as any event occurring during the study not before exposure to study vaccine or any event already present that worsens after exposure to study vaccine. [Note: worsening of a pre-existing condition after vaccination will be reported as a new AE.]

Adverse events will also be evaluated by the investigator for the coexistence of MAAE which is defined as an AE that leads to an unscheduled visit to a healthcare practitioner.

Overview of unsolicited AEs will be summarized by stage, up to 28 days after vaccination and throughout the study (see [Section 6.1](#)).

All summary tables (except for the overall summary of AEs) for unsolicited AEs will be presented by SOC and PT for TEAEs with counts of subjects included. SOC will be displayed in internationally agreed order. PT will be displayed in alphabetical order for first booster, in descending order of frequency based on the mRNA-1273 50 µg group then alphabetically for second booster, and in descending order of frequency based on the mRNA-1273.231 50 µg group then alphabetically for third booster. When summarizing the number and percentage of subjects with an event, subjects with multiple occurrences of the same AE or a continuing AE will be counted once. Subjects will be presented according to

the highest severity in the summaries by severity, if subjects reported multiple events under the same SOC and/or PT.

Percentages will be based upon the number of subjects in the Safety Set.

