7.4.4. Medically Attended Adverse Events

An MAAE is an AE that leads to an unscheduled visit to an HCP. This would include visits to a study site for unscheduled assessments (eg, abnormal laboratory follow-up, COVID-19 [[Section 7.1.6](#)]) and visits to HCPs external to the study site (eg, urgent care, primary care physician). Investigators will review unsolicited AEs for the occurrence of any MAAEs. Unsolicited AEs will be captured on the AE page of the eCRF.

All confirmed COVID-19 cases will be recorded as MAAEs.

All suspected cases of anaphylaxis should be recorded as MAAEs and reported as an SAE, based on the criteria for a medically important event, unless the event meets other serious criteria. As an SAE, the event should be reported to the Sponsor or designee immediately and in all circumstances within 24 hours per [Section 7.4.11](#). The investigator will submit any updated anaphylaxis case data to the Sponsor within 24 hours of it being available. For reporting

purposes, a participant who displays signs or symptoms consistent with anaphylaxis (as follows) should be reported as a potential case of anaphylaxis. This is provided as general guidance for investigators and is based on the Brighton Collaboration case definition ([Rüggeberg et al 2007](#)).

Anaphylaxis is an acute hypersensitivity reaction with multi-organ system involvement that can present as, or rapidly progress to, a severe life-threatening reaction. It may occur following exposure to allergens from a variety of sources.

Anaphylaxis is a clinical syndrome characterized by the following:

- Sudden onset AND
- Rapid progression of signs and symptoms AND
- Involves 2 or more organ systems, as follows:
 - **Skin/mucosal:** urticaria (hives), generalized erythema, angioedema, generalized pruritus with skin rash, generalized prickle sensation, and red and itchy eyes.
 - **Cardiovascular:** measured hypotension, clinical diagnosis of uncompensated shock, loss of consciousness or decreased level of consciousness, and evidence of reduced peripheral circulation.
 - **Respiratory:** bilateral wheeze (bronchospasm), difficulty breathing, stridor, upper airway swelling (lip, tongue, throat, uvula, or larynx), respiratory distress, persistent dry cough, hoarse voice, sensation of throat closure, sneezing, and rhinorrhea.
 - **Gastrointestinal:** diarrhea, abdominal pain, nausea, and vomiting.

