7.4.7. Eliciting and Documenting Adverse Events

The investigator is responsible for ensuring that all AEs and SAEs are recorded in the eCRF and reported to the Sponsor.

Solicited ARs will be collected from Day 1 through 7 days after vaccination. Other (unsolicited) AEs will be collected from Day 1 through 28 days after vaccination.

The MAAEs, AESI, AE leading to withdrawal, AESI, and SAEs will be collected from participants as specified in the SoE ([Table 17](#), [Table 18](#), [Table 19](#), and [Table 20](#)) until the end of their participation in the study. Any AEs occurring before receipt of IP will be analyzed separately from AEs occurring after receipt of the study vaccine.

At every study site visit or telephone contact, participants will be asked a standard question to elicit any medically related changes in their well-being (including COVID-19 symptoms) according to the scripts provided. Participants will also be asked if they have been hospitalized, had any accidents, used any new medications, changed concomitant medication regimens (both prescription and over-the-counter medications), or had any non-study vaccinations.

In addition to participant observations, physical examination findings, or other documents relevant to participant safety classified as an AE will be documented on the AE page of the eCRF.

After the initial AE/SAE report, the investigator is required to proactively follow each participant at subsequent visits/contacts. All AEs and SAEs will be treated as medically appropriate and followed until resolution, stabilization, the event is otherwise explained, or the participant is LTFU (as defined in [Section 6.3](#)).

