7.4.10. Reporting Adverse Events

The investigator is responsible for reporting all AEs that are observed or reported during the study, regardless of their relationship to IP or their clinical significance. If there is any doubt as to whether a clinical observation is an AE, the event should be reported.

All unsolicited AEs reported or observed during the study will be recorded on the AE page of the eCRF. Information to be collected includes type of event, time of onset, investigator-specified assessment of severity (impact on activities of daily living) and relationship to IP, time of resolution of the event, seriousness, as well as any required treatment or evaluations, and outcome. The unsolicited AEs resulting from concurrent illnesses, reactions to concurrent illnesses, reactions to concurrent medications, or progression of disease states must also be reported. All AEs will be followed until they are resolved or stable or judged by the investigator to be not clinically significant. The Medical Dictionary for Regulatory Activities (MedDRA) will be used to code all unsolicited AEs.

Any medical condition that is present at the time of screening but does not deteriorate should not be reported as an unsolicited AE. However, if it deteriorates at any time during the study, it should be recorded as an unsolicited AE.

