6.3.1.1. Incidence of Adverse Events

An overall summary of unsolicited TEAEs including the number and percentage of subjects who experience the following will be presented:

- Any unsolicited TEAEs
- Any serious TEAEs
- Any fatal TEAEs
- Any unsolicited medically-attended TEAEs
- Any unsolicited TEAEs leading to discontinuation from participation in the study
- Any unsolicited severe TEAEs
- Any unsolicited AESIs
- Any unsolicited non-serious TEAEs
- Any unsolicited severe non-serious TEAEs

The table will also include number and percentage of subjects with unsolicited TEAEs that are treatment-related per PI's assessment in each of the above categories.

In addition, separate listings containing individual subject adverse event data for unsolicited AEs, unsolicited TEAEs leading to discontinuation from participation in the study, serious AEs and fatal unsolicited AEs will be provided separately.

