6.3.1.2. TEAEs by System Organ Class and Preferred Term

The following summary tables of TEAEs will be provided by SOC and PT using frequency counts and percentages (i.e., number and percentage of subjects with an event), up to 28 days after vaccination. Select TEAEs that will be collected throughout the study will also be summarized throughout the study when applicable:

- All unsolicited TEAEs
- All unsolicited TEAEs that are treatment-related

- All serious TEAEs
- All serious TEAEs that are treatment-related
- All unsolicited TEAEs leading to discontinuation from participation in the study
- All unsolicited severe TEAEs
- All unsolicited severe TEAEs that are treatment-related
- All unsolicited medically-attended TEAEs
- All unsolicited medically-attended TEAEs that are treatment-related
- All unsolicited AESIs
- All unsolicited AESIs that are treatment-related

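### The throughout-study adverse event overview includes rows for any and for non-serious unsolicited events, although their scheduled collection stops at 28 days

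*SAP*

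**What the plan says.** SAP 6.3.1 sets two periods for the overview: "Overview of unsolicited AEs will be summarized by stage, up to 28 days after vaccination and throughout the study". SAP 6.1 defines the second as running from Day 1 to the earliest of study completion, discontinuation or death. SAP 6.3.1.1 lists nine rows, among them "Any unsolicited TEAEs", "Any unsolicited severe TEAEs", a non-serious row and "Any unsolicited severe non-serious TEAEs", each with a treatment-related version. No row is tied to one period. Percentages use the number of subjects in the Safety Set.

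On collection, protocol 7.4.7 says: "Other (unsolicited) AEs will be collected from Day 1 through 28 days after vaccination". Protocol 7.1 and 7.4.12 also set a 28-day window. The schedules of events (Tables 17 to 20) mark recording of unsolicited AEs only at Days 1, 8, 15 and 29. The SAP's own unsolicited AE endpoint (3.1) covers 28 days. Protocol 7.1 and 7.1.1 continue SAEs, MAAEs, AESIs and AEs leading to withdrawal to the end of study.

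For the tables by system organ class and preferred term, SAP 6.3.1.2 is more careful: "Select TEAEs that will be collected throughout the study will also be summarized throughout the study when applicable".

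**The concern.** A percentage headed as throughout the study invites reading as the share of participants with an event over 6 or 12 months. That holds only for event types sought in the same way for the whole period. The rows for any and for non-serious unsolicited TEAEs do not meet this condition, and the SAP applies the needed limit to the detailed tables but not to the overview above them.

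Safety is a primary objective in every Part, so the overview will be read closely. Follow-up length also differs between arms that may be set side by side. The mRNA-1273 50 µg arm of Part F is followed for 12 months and Part H for 6. SAP 6.3.1 sorts second-booster tables by frequency in the mRNA-1273 50 µg group, which suggests, without stating it, that these arms will share a table.

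**Working it through.** The plan gives no figure to reproduce. The check sets each row's reporting period against its collection window.

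**Step 1: rows against collection after Day 28**

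| Overview row (SAP 6.3.1.1) | Scheduled collection after Day 28 (protocol 7.1, 7.1.1, 7.4.7, Tables 17–20) | Throughout-study percentage |
|---|---|---|
| Serious, fatal | Yes, as SAEs | Period and collection agree |
| Medically attended, AESI, leading to discontinuation | Yes | Period and collection agree |
| Any unsolicited | Only if SAE, MAAE, AESI or leading to withdrawal | Full to Day 28, selective afterwards |
| Non-serious | Only if MAAE, AESI or leading to withdrawal | Full to Day 28, selective afterwards |
| Severe, severe non-serious | Same classes, but see step 2 | Largely ascertained |

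**Step 2: the severe rows.** Protocol 7.4.8 defines a severe unsolicited AE as one that prevents daily activity and needs intensive therapeutic intervention. Under protocol 7.4.4, an AE leading to an unscheduled visit to a healthcare provider is an MAAE. Most severe events after Day 28 should therefore be captured as MAAEs or SAEs, so these rows are much less affected than the any and non-serious rows.

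**Step 3: share of follow-up with full collection**
- Parts A.1, B, C, D, F and G: 28 / 366 = 0.077, or 7.7%.
- Parts A.2, H and J: 28 / 181 = 0.155, or 15.5%.

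These are shares of time, not of events. Part E is left out because its collection rules are in a site-specific amendment.

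**Step 4: unequal follow-up.** The selective phase lasts 366 − 28 = 338 days in the Part F mRNA-1273 arm and 181 − 28 = 153 days in Part H. It is 338 / 153 = 2.2 times as long in the first. The percentages use subjects, not person-time, so nothing in the table adjusts for this.

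**Step 5: is later capture absent?** No. The call script in protocol 7.1.2 lists AEs alongside the special classes, with calls to Day 169 or Day 349. Protocol 7.4.7 also has a standard question about health changes at each visit or call. Protocol 7.4.10 adds: "All unsolicited AEs reported or observed during the study will be recorded on the AE page of the eCRF". These passages conflict with the 28-day window. A site following 7.4.10 would enter later events that a site following the schedule of events would not.

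**The case against.** The strongest reply is that participants are still asked about AEs after Day 28 and that the consequences are small. SAP 6.1 makes 28 days the primary period for unsolicited AEs, a 28-day overview is also planned, safety is descriptive, and AE listings are provided. The SAP never calls these rows a 6- or 12-month rate, and SAP 6.3.1.2 does not name the rows to which its limit applies.

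All of this stands, and it limits the weight of the point. It does not remove the two rows from the throughout-study display, and conflicting collection instructions do not give complete ascertainment.

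A reader might infer three stronger things that the documents do not support:
- **That nobody asks about other AEs after Day 28.** Protocol 7.1.2, 7.4.7 and 7.4.10 show otherwise.
- **That arm differences in these rows reflect only COVID-19 cases.** Protocol 7.4.4 does say "All confirmed COVID-19 cases will be recorded as MAAEs", and SAP 6.4.3 dates enrollment of the Part F mRNA-1273 arm to February 2022 and of Part H to August 2022. Case counts may therefore contribute. But every throughout-study row also contains all the 28-day events. The medically attended row carries the same influence and stays in the table under the fix.
- **That most AEs are missed.** The documents give no AE rate for the later months. The 28-day figures in protocol 1.4.2 come from the primary series in another trial, and extending them to a year would need a constant hazard that nothing here supports.

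**Conclusion.** The mismatch is in the current text. The throughout-study rows for any and for non-serious unsolicited TEAEs, with their treatment-related versions, join full 28-day ascertainment to selective and possibly site-dependent capture for the remaining 153 or 338 days. They should not be read as 6- or 12-month incidence or compared between arms with different follow-up. The severe rows are affected far less.

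This rests on taking the specific collection sections and the schedules of events as governing over the general rule in protocol 7.4.10. How many events are involved cannot be determined from the documents. The point is minor: no hypothesis, sample size or 28-day safety result changes.

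**What to change.** In SAP 6.3.1 and 6.3.1.1, extend the limit of SAP 6.3.1.2 to the overview:
- Show the any and non-serious unsolicited rows, with their treatment-related versions, for the 28-day period only.
- Keep the serious, fatal, medically attended, AESI and discontinuation rows for both periods.
- The severe and severe non-serious rows may stay for both periods, with a footnote that after Day 28 they include only events captured as MAAE, SAE, AESI or leading to withdrawal.

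Reconcile protocol 7.1.2 and 7.4.10 with the 28-day window, so that the footnote is accurate and it is clear what sites were to record after Day 28.

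The cost is a short SAP edit, one footnote and a protocol clarification. The loss is that no study-long figure for any unsolicited TEAE is shown. The planned AE listings are unaffected.
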